1.3. Novel lung ventilation imaging based on 4D CT has high translational potential and advantages

4D CT ventilation imaging is a novel promising technique (Guerrero *et al.*, 2005) (Figure 1) that has high translational potential and advantages (e.g., higher resolution, lower cost, and/or greater availability) over competing modalities. Thus, there has been growing interest in using this technology for functional avoidance treatment planning (Yaremko *et al.*, 2007; Yamamoto *et al.*, 2011) and treatment/toxicity assessment (Ding *et al.*, 2010; Vinogradskiy *et al.*, 2012). Animal studies have demonstrated high accuracy, e.g., correlation with xenon (Xe)-CT ventilation as reference (Fuld *et al.*, 2008; Reinhardt *et al.*, 2008; Ding *et al.*, 2012) as well as high reproducibility (Du *et al.*, 2012). Human studies have reported relatively inconsistent results (Castillo *et al.*, 2010; Castillo *et al.*, 2012; Du *et al.*, 2012; Mathew *et al.*, 2012; Yamamoto *et al.*, 2012; Yamamoto *et al.*, 2014), but reasonable correlations with PFT parameters (Yamamoto *et al.*, 2014), SPECT ventilation (Yamamoto *et al.*, 2014), hyperpolarized ³He MR ventilation (Mathew *et al.*, 2012) and SPECT perfusion (Castillo *et al.*, 2012) indicate the potential for 4D CT ventilation imaging to have physiological significance.

[figure not shown]

Figure 1. Schematic diagram for 4D CT ventilation imaging through (1) acquisition of 4D CT scans, (2) spatial mapping of different respiratory phases of 4D CT images using DIR, deriving a displacement vector field, and (3) analysis of the resultant displacement vector field to quantify regional volume change, a surrogate for ventilation.

1.4. We propose a novel paradigm, 4D CT ventilation image-guided personalized radiotherapy to improve therapeutic gains

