Many investigators have demonstrated a dosimetric benefit of functional image-guided radiotherapy that avoids high-functional lung regions using various modalities, including SPECT perfusion (Marks *et al.*, 1995), hyperpolarized gas magnetic resonance (MR) ventilation (Ireland *et al.*, 2007) and 4D CT ventilation (Yaremko *et al.*, 2007; Yamamoto *et al.*, 2011). We have demonstrated that 4D CT ventilation image-guided radiotherapy planning reduces the mean dose to high-functional lung regions by 2 Gy on average compared to anatomic image-guided planning (Yamamoto *et al.*, 2011), indicating that 4D CT ventilation image-guided radiotherapy is estimated to reduce pneumonitis by 4%, corresponding to over 5,000 patients/year in the US, based on the fact that about 60% (Tyldesley *et al.*, 2001) of 221,130 new lung cancer patients (Siegel *et al.*, 2011) are treated with radiotherapy. It is assumed that the probability of pneumonitis increases with the mean dose to high-functional lung regions in a similar manner to the published data on the mean dose to the total lung (Marks *et al.*, 2010). There have been no attempts to assess the safety/feasibility or clinical significance of such treatment in human subjects. In this clinical trial, we will assess the safety and feasibility of 4D CT ventilation image-guided personalized radiotherapy. We will deliver personalized radiotherapy treatments for lung cancer patients, and follow up patients to assess the safety and feasibility. The hypothesis to be tested is: *4D CT ventilation image-guided personalized radiotherapy can be delivered safely for lung cancer.*

2. Specific Objectives and Hypotheses

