4.1. Scans to be acquired

Patients will be positioned in the supine position on a flat tabletop with immobilization (a customized thermoplastic immobilization cast or a molded foam cradle for stabilization for CFRT; a stereotactic body frame or BodyFIX system for SABR). Abdominal compression will be used for all SABR patients unless tumor motion < 1 cm can be reliably demonstrated by fluoroscopy and confirmed by 4D CT without compression. The following scans will be obtained:

Simulation imaging

- 1) Free-breathing CT extending from the angle of the mandible cranially to the inferior extent of the liver caudally at a slice thickness of ≤ 3 mm for CFRT and ≤ 2 mm for SABR. IV contrast to assist in delineation of the mediastinal nodal regions is permitted but not required.
- 2) Pre-treatment 4D CT scan to include lungs from apices to diaphragm and full disease extent.
- 3) If abdominal compression is used, an additional 4D CT scan will be acquired without abdominal compression.

During a course of treatment (CFRT only)

- 1) Two mid-treatment free-breathing CT scans performed at 16-20 Gy and 30-34 Gy to include lungs from apices to diaphragm and full disease extent based on the same method as simulation.
- 2) Two mid-treatment 4D CT scans performed with the mid-treatment free-breathing CT scans to include lungs from apices to diaphragm and full disease extent.

4.2. 4D CT ventilation computation

4D CT ventilation images at the peak-inhale phase will be created using a software tool developed and provided by a collaborator, [name] at Philips Research. This software has not received regulatory clearance. This tool loads anonymized 4D CT images acquired at UC Davis as input, and provides ventilation images calculated based on a non-parametric/volumetric DIR algorithm (Staring *et al.*, 2010) and two classes of ventilation metric: Hounsfield unit (HU)-change (Simon, 2000; Fuld *et al.*, 2008) and Jacobian (Reinhardt *et al.*, 2008) as output.

5. Radiation Therapy

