5.4.2. Lungs

We will create 4D CT ventilation image-guided personalized radiotherapy plans that selectively avoid irradiating highly-functional lung regions. The peak-inhale 4D CT ventilation image will be aligned with the free-breathing CT image (primary image set for treatment planning) by rigid image registration. The overlapped lungs between the free-breathing CT and peak-inhale 4D CT images will be contoured. Note that the final total lung volume for dose-volume analysis will include combined right and left lungs, excluding the GTV, trachea, and main and lobar bronchi. IMRT or VMAT optimization will be performed by setting higher weights to highly-functional lung regions than poorly-functional regions to meet the dose-volume constraints shown below.

CFRT

Tissue	Constraints
Lung (right and left minus CTV)	$V_{20} < 37\%$ (<40% will be scored as a minor deviation) Mean lung dose (MLD) <20 Gy (<21 Gy will be scored as a minor deviation) Functional $V_{20} < 30\%$ (Vinogradskiy et al. , 2013) (<33% will be scored as a minor deviation) Functional MLD <19 Gy (Vinogradskiy et al. , 2013) (<20 Gy will be scored as a minor deviation)

SABR

Tissue	3 fraction			5 fraction		
	Volume	Vol Max	Max to 0.03 cc	Volume	Vol Max	Max to 0.03 cc
Lung (right and left minus CTV)	<1500 cc	10.5 Gy*	NA	<1500 cc	12.5 Gy*	NA
	<1000 cc	11.4 Gy*		<1000 cc	13.5 Gy*	
	Functional $V_{20} < 4\%$ (Barriger et al. , 2012) (<7% will be scored as a minor deviation) Functional MLD <4 Gy (Barriger et al. , 2012) (<5 Gy will be scored as a minor deviation)					

*Constraints marked by asterisk are guidelines and will not be scored as a protocol deviation if not achieved. For SABR in patients with more than one target, the lung dose-function constraints (functional MLD and V20) are guidelines and will not be scored as a protocol deviation if not achieved. **Other constraints represent absolute limits and treatment delivery that cannot meet these constraints will constitute a major protocol violation.**

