To quantify the dosimetric significance of 4D CT ventilation image-guided adaptive radiotherapy, we will create: (1) 4D CT ventilation image-guided adaptive radiotherapy plan, (2) 4D CT ventilation image-guided non-adaptive radiotherapy plan, and (3) anatomical image-guided non-adaptive radiotherapy plan. We will evaluate the lung functional dose-volume parameters, including the functional V_x (fV_x) (% volume receiving $\geq x$ Gy) and functional mean lung dose (fMLD) for each plan. The lung functional dose-volume parameters of the 4D CT ventilation image-guided adaptive radiotherapy plans will be compared with those of the 4D CT ventilation image-guided non-adaptive radiotherapy plans and anatomical image-guided non-adaptive radiotherapy plans using a paired *t*-test. Furthermore, we will also investigate sensitivity to the number (1 or 2) and time (16-20 Gy and/or 30-34 Gy) of plan adaptation to design an optimal adaptive radiotherapy strategy, *e.g.*, when and how many time(s) to adapt the original plan.

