There will be no additional costs to subjects because of participation in this study.

17. Sharing of Results with Subjects

The results of this study will not be shared with subjects or subjects' primary care physicians.

18. Devices

In vivo EPID dosimetry with the PerFRACTION software calculates the dose of the day reconstructed from EPID measurements in patient anatomy using the treatment plan CT image data. The calculated dose of the day will be compared with the plan dose to estimate changes in patient anatomy. The performance of in vivo EPID dosimetry will be evaluated by comparing the PerFRACTION analysis results with the dose of the day calculated with the mid-treatment CT image data as reference. This device poses no additional risk to subjects.

REFERENCES

Abratt R P, Willcox P A and Smith J A 1990 Lung cancer in patients with borderline lung functions--zonal lung perfusion scans at presentation and lung function after high dose irradiation *Radiother Oncol* **19** 317-22

- Bradley J, Graham M V, Winter K, Purdy J A, Komaki R, Roa W H, Ryu J K, Bosch W and Emami B 2005a Toxicity and outcome results of RTOG 9311: a phase I-II dose-escalation study using three-dimensional conformal radiotherapy in patients with inoperable non-small-cell lung carcinoma *Int J Radiat Oncol Biol Phys* **61** 318-28
- Bradley J D, Graham M, Suzanne S, Byhardt R, Govindan R, Fowler J, Purdy J, Michalski J, Gore E and Choy H 2005b Phase I results of RTOG L-0117; a phase I/II dose intensification study using 3DCRT and concurrent chemotherapy for patients with Inoperable NSCLC *J Clin Oncol* **23** 7063 (Abstract)

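### Section 9.3 compares plans on the functional dose they were optimised to lower, without naming the scoring image or scoring on any image not used for planning

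*Combined protocol and SAP*

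**What the plan says.** Section 5.4.2 sets out how the ventilation-guided plans are made. One peak-inhale ventilation image is registered to the planning CT, and "IMRT or VMAT optimization will be performed by setting higher weights to highly-functional lung regions than poorly-functional regions".

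Section 9.3 defines three plans: (1) ventilation-guided adaptive, (2) ventilation-guided non-adaptive and (3) anatomical non-adaptive. On the outcome it says "We will evaluate the lung functional dose-volume parameters, including the functional" Vx and functional mean lung dose (fMLD). It then states the comparison: "The lung functional dose-volume parameters of the 4D CT ventilation image-guided adaptive radiotherapy plans will be compared with those of the" plans numbered (2) and (3) here, by paired t-test. The same paragraph uses the result to explore whether to adapt once or twice, and at 16-20 Gy, 30-34 Gy or both.

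Section 4.1 provides, for CFRT patients only, "Two mid-treatment 4D CT scans performed with the mid-treatment free-breathing CT scans". With the simulation 4D CT, each CFRT patient therefore has three scans from which a ventilation image can be made. On image quality, Section 1.3 says "Human studies have reported relatively inconsistent results", then lists reasonable correlations with other measures of lung function.

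No section names the image that scores each plan, sets one aside, or allows for image reproducibility.

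**The concern.** A plan told to lower dose where the ventilation image is bright also lowers dose where the image is bright only by error. Scored on that same image, both parts count as functional sparing, but only the first is a benefit to the patient. The anatomical plan was not fitted to the image and gets no such credit.

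The paired t-test gives no protection, because the bias has the same sign in every patient. The test only asks whether the mean difference on the chosen scoring image is non-zero.

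For adaptive versus non-adaptive, the choice of scoring image can by itself favour one plan or the other. This contrast is the only analysis given for secondary objective 4, and it feeds the choice of when and how often to adapt.

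**Working it through.** **The plan's own figure.** Section 9.3 states no effect size, SD or power for this comparison. The nearest figure is background in Section 1.4: ventilation-guided planning "reduces the mean dose to high-functional lung regions by 2 Gy on average", projected to a 4% reduction in pneumonitis. The projection reproduces: 221,130 × 0.60 × 0.04 = 5,307, matching the stated figure of over 5,000 patients a year. It concerns a different contrast and is not used below.

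**Gain on the planning image and on another image.** Let m be measured ventilation by voxel and d the dose.

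- fMLD = Σmd/Σm = mean(d) + Cov(m,d)/mean(m).
- Suppose the ventilation-guided dose is d = d0 − k(m − mean m), with d0 the anatomical dose.
- Gain over the anatomical plan, scored on m: G = k·Var(m)/mean(m).
- Gain scored on a repeat image m′ with the same mean and variance: k·Cov(m,m′)/mean(m) = r·G, where r is the repeat-image correlation.
- If m is true ventilation plus independent error, r = Var(true)/Var(m), and the true gain is also r·G.

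**Three images and two adaptations.** 60 Gy in 30 fractions is 2 Gy per fraction. The scan windows are then 8-10 and 15-17 fractions, as in Appendix III. Adapting at the midpoints (9 and 16) gives segments of 9, 7 and 14 fractions. Assume each segment is planned on the latest image and that ventilation does not really change. The values of r are assumptions. Entries are multiples of G.

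| Contrast and scoring image | Formula | r = 0.5 | r = 0.7 | r = 0.9 |
|---|---|---|---|---|
| Adaptive vs anatomical: truth | r | 0.50 | 0.70 | 0.90 |
| each segment on its own planning image | 1 | 1.00 | 1.00 | 1.00 |
| all on simulation image | 9/30 + (21/30)r | 0.65 | 0.79 | 0.93 |
| all on first mid-treatment image | 7/30 + (23/30)r | 0.62 | 0.77 | 0.92 |
| all on second mid-treatment image | 14/30 + (16/30)r | 0.73 | 0.84 | 0.95 |
| each segment on an image not used for it | r | 0.50 | 0.70 | 0.90 |
| Adaptive vs non-adaptive: truth | 0 | 0 | 0 | 0 |
| both on the image current for each segment | +(21/30)(1 − r) | +0.35 | +0.21 | +0.07 |
| both on simulation image | −(21/30)(1 − r) | −0.35 | −0.21 | −0.07 |
| both on second mid-treatment image | +(14/30)(1 − r) | +0.23 | +0.14 | +0.05 |

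Simulations of the same model agree with these formulas. Two results matter:

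- Every acquired CFRT image feeds the twice-adapted plan. Scoring that whole plan on any one of them is therefore partly self-scoring. Segment-by-segment scoring on an unused image is not.
- With no true benefit from adapting, the sign of the adaptive versus non-adaptive difference is set by the scoring image. If each plan is scored on its own planning image, the error terms cancel in this model (G − G = 0), but the two plans are then measured on different scans.

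**Dependence on spatial structure.** Suppose dose follows a smoothed image Sm, with T the true signal and E the error. The ratio of cross-image to same-image gain is Cov(T,ST)/[Cov(T,ST) + Cov(E,SE)]. If E is as smooth as T, this equals r. If E is voxel-level noise, smoothing nearly removes Cov(E,SE) and the ratio approaches 1. At r = 0.5 the ratio therefore runs from about 0.5 to about 1.0.

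**The case against.** Several points on the other side stand.

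- **Silence is not self-scoring.** A reader might infer that each plan will be scored on the image it was fitted to. Section 9.3 does not say so, and it uses composite plans for functional dose in the toxicity correlation. The documented defect is an omission. It still matters, because scoring a twice-adapted plan on any single acquired image is partly self-scoring.
- **Direction.** A reader might infer that the gain from adaptation is overstated. Upward bias is clear only against the anatomical plan; against the non-adaptive plan it can go either way.
- **Size.** It is tempting to discount the 2 Gy and 4% in Section 1.4 by an assumed correlation. The documents do not support that. Those figures come from a planning study of ventilation-guided versus anatomical plans, its scoring image is not described, and no reliability is given. Target coverage and organ constraints also limit how closely dose can follow the image.
- **Image quality.** The remark on inconsistent human results is followed by reasonable correlations with lung function tests, SPECT and MR. Any systematic error of the method would recur on a repeat image, so cross-scoring would not reveal it.
- **Limits of a repeat image.** Mid-treatment images carry real ventilation change, which is the reason to adapt. Resting the conclusion on them alone would be a choice of estimand. The 30-34 Gy image is unused for a single adaptation at 16-20 Gy, but it is a planning image for the other strategies.
- **Status.** Section 9.3 calls the secondary analyses primarily descriptive. That lowers the stakes, but a descriptive estimate can still be biased, and this one comes with a test and a choice of strategy.

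**Conclusion.** The point holds as an omission with a predictable consequence. Section 9.3 scores plans on the quantity that the ventilation-guided plans were built to lower, names no scoring image, and makes no use of the repeat images to check the result.

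If plans are scored on their own planning images, the gain over the anatomical plan is biased upward. The adaptive versus non-adaptive difference can be biased in either direction. Both statements assume that the image contains error and that dose responds to it.

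No size can be put on the bias from the documents. The table shows direction and mechanism under a linear, voxel-by-voxel response with assumed reliability and no real change over time; it is not a forecast for this trial.

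The point is confined to CFRT patients, whose number is not stated, and to a secondary, mainly descriptive analysis. The primary safety endpoints are unaffected. It should be settled in Section 9.3 before the plans are compared.

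**What to change.** Amend Section 9.3, for CFRT patients:

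- **Common scoring.** Evaluate all three plans on the same prespecified CT and ventilation image set, with plans (2) and (3) recalculated on the mid-treatment CTs.
- **Cross-image sensitivity analysis, prespecified.** Also score each plan, or each plan segment, on an acquired ventilation image not used to optimise it. Examples are the 16-20 Gy and 30-34 Gy images for plans (2) and (3), and the 30-34 Gy image for a single adaptation at 16-20 Gy.
- **Reporting.** Give same-image and cross-image differences side by side, and qualify the conclusion on adaptation if they disagree.

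**Cost.** No new scans, patients or treatment changes; the work is extra dose recalculation by the physics team. Section 18 already plans a comparison with "the dose of the day calculated with the mid-treatment CT image data as reference". That concerns delivered treatment, so the undelivered anatomical and alternative adaptive plans would be additional work.

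**Limits to state in the plan.** Repeat images mix real ventilation change with error and share any systematic error of the method. No single unused image serves every adaptation strategy. Mid-treatment repeats do not exist for stereotactic patients, whose only possible second scan is one without abdominal compression.

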9.4. Sample size

We will examine the safety of 4D CT ventilation image-guided personalized radiotherapy based on AEs during the first 12 months of follow-up and toxicity-related drop-out. With a sample size of 34 patients, we will be able to see grade ≥ 3 radiation pneumonitis, grade ≥ 3 esophagitis and other grade ≥ 3 AEs at least once with 94%, 99% and 99% probabilities, respectively, assuming

true rates of 13%, 21% and 20%, respectively. We can also estimate these AE rates with a standard error of 8%, 9% and 9%, respectively.

Approximately 37% of patients are estimated to die over the first 12 months of follow-up according to the published survival data for patients with locally advanced NSCLC (Machtay *et al.*, 2012). Also 1% of patients are estimated to drop out for reasons unrelated to the protocol treatment. To compensate for possible loss of patients for such reasons, a sample size of 34 (increased by 38% from 20) will be used.

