9.2. Patient accrual

We aim to accrue 34 patients over 1.5 years. Patient accrual will continue until either the projected sample of 34 patients has been enrolled, or the number of patients developing Grade ≥ 3 AEs or drop-out due to intolerance of treatment exceeds five. Patient follow-up will continue until all patients have at least two years of follow-up, to allow for assessment of longer-term AEs.

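### Section 9.4 attaches to 34 patients the detection probabilities and standard errors of 20, and misdescribes the step from 20 to 34 as a 38% increase

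*Combined protocol and SAP*

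**What the plan says.** Section 9.4 of the combined protocol and SAP bases the sample size on two quantities: the chance of observing each type of grade 3 or higher event at least once, and the standard error of each estimated rate.

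- The sentence begins "With a sample size of 34 patients, we will be able to see grade" and continues that each event type will be seen "at least once with 94%, 99% and 99% probabilities, respectively". The order is pneumonitis, esophagitis, other events, assuming "true rates of 13%, 21% and 20%, respectively".
- It adds: "We can also estimate these AE rates with a standard error of 8%, 9% and 9%, respectively".
- The following paragraph turns to losses: "Approximately 37% of patients are estimated to die over the first 12 months of follow-up", and a further "1% of patients are estimated to drop out for reasons unrelated to the protocol treatment".
- It concludes: "To compensate for possible loss of patients for such reasons, a sample size of 34 (increased by 38% from 20) will be used".

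Section 9.2 gives the same enrolment target: "We aim to accrue 34 patients over 1.5 years". Nothing in 9.4 says that the probabilities and standard errors refer to any number other than 34.

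**The concern.** The plan states no power or type I error for the primary endpoints, so these six figures are its only quantitative support for the sample size. A colleague who recomputes them at 34 gets different answers. One who applies the stated 38% increase to 20 gets 28 patients, not 34. As written, neither the precision nor the enrolment target can be reproduced from the text.

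Two questions follow: which sample size do the six figures belong to, and is 34 itself wrong or only its description? The first decides what precision the trial can claim. The second decides whether enrolment has to change.

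**Working it through.** **Inputs, all from section 9.4:** true rates p = 0.13, 0.21 and 0.20; labelled sample size 34; base number 20; expected deaths 37% and unrelated drop-out 1%, together 38%.

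**Formulas.** Probability of at least one event: 1 − (1 − p)^n. Standard error of an estimated rate: √(p(1 − p)/n).

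**Step 1: reproduce the stated figures.** For pneumonitis at n = 20, 1 − 0.87^20 = 1 − 0.0617 = 93.8%, and √(0.13 × 0.87/20) = 7.5%. At n = 34, 1 − 0.87^34 = 1 − 0.0088 = 99.1%, and √(0.13 × 0.87/34) = 5.8%. The same calculation for all three event types gives:

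| n | P(at least one): pneumonitis / esophagitis / other | Standard error: pneumonitis / esophagitis / other |
|---|---|---|
| Stated, labelled 34 | 94% / 99% / 99% | 8% / 9% / 9% |
| 19 | 92.9% / 98.9% / 98.6% | 7.7% / 9.3% / 9.2% |
| 20 | 93.8% / 99.1% / 98.8% | 7.5% / 9.1% / 8.9% |
| 21 | 94.6% / 99.3% / 99.1% | 7.3% / 8.9% / 8.7% |
| 34 | 99.1% / 99.97% / 99.95% | 5.8% / 7.0% / 6.9% |

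Every n from 10 to 44 was tried. Only n = 20 rounds to all six stated values. At 19 the pneumonitis probability rounds to 93%. At 21 it rounds to 95% and its standard error to 7%. At 34 none of the six agrees after rounding.

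**Step 2: test the stated enlargement.**

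- A 38% increase on 20: 20 × 1.38 = 27.6, so 28.
- The actual step: 34/20 = 1.70, a 70% increase.
- Allowing for a 38% loss: 20/(1 − 0.38) = 20/0.62 = 32.3, so at least 33.
- Treating deaths and drop-out as successive losses: 20/(0.63 × 0.99) = 32.1, so again 33.
- Patients expected to remain from 34: 34 × 0.62 = 21.1.

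So 34 exceeds the minimum of 33 by one patient. The 38% is a loss from the enrolled number, not an increase on the base.

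**Step 3: size of the discrepancy.** The ratio of the standard errors is √(34/20) = 1.30, so the stated values are those of a sample with standard errors about 30% larger than 34 patients would give. The chance of seeing no pneumonitis is 6.2% at 20, 5.4% at 21 and 0.9% at 34.

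**The case against.** The best defence is that the two paragraphs of 9.4 belong together. On that reading 34 is the number enrolled, the figures describe what is left after losses, and 38% is the loss allowance loosely called an increase. The 21 patients expected to remain give 94.6% and 7.3% for pneumonitis, within one percentage point of the stated 94% and 8%. The label is also conservative, since it understates what 34 fully observed patients would give. This limits the consequence but does not rescue the text. The reader has to work backwards to find that 20 is meant, because the sentence names 34 and the losses come only afterwards. Even on this reading the figures match 20, not 21.

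A second objection has more force. The plan defines no evaluable set. Section 9.3 does not remove patients who die from the denominator, section 11.3 continues follow-up after treatment stops, and section 11.5 excludes data only on withdrawal of consent. Section 7.3 says severe esophagitis usually peaks 4 to 8 weeks from the start of treatment, so many patients who die later in the year would already have been observed for it. For that endpoint the effective number could be close to 34. This stands as a question the sponsor should answer. It does not displace 20 as the default reading, because 9.4 itself treats deaths within 12 months as losses to be made up.

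Third, finding 34 sufficient must not be read too widely. It is enough to keep at least 20 patients after a 38% loss. It is not thereby enough to show that the rates lie below the limits in 9.3: with 4 pneumonitis events in 34 patients the exact 95% interval runs from about 3% to 27%, against a limit of 13%.

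**Conclusion.** The point holds, at minor severity. The six figures in 9.4 are those of 20 patients and are labelled as those of 34. The largest gaps are 94% against 99.1% for detecting pneumonitis and 8% against 5.8% for its standard error. The description of the enlargement is also false: the step is 70%, and 38% is the expected loss. The target of 34 is consistent with that loss, and section 9.2 agrees with it.

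This rests on the plan's own rates and its own 38% loss, on simple binomial formulas, and on treating patients who die or drop out within 12 months as not evaluable, as 9.4 does. The effect is confined to the justification. The limits of 13%, 21% and 20% in 9.3 and the accrual stop in 9.2 do not use these figures.

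**What to change.** Make two wording changes in 9.4.

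1. Replace the labelled sample size with the number the figures belong to:

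> With 20 patients evaluable at 12 months, the probabilities of observing at least one event are 94%, 99% and 99%, and the standard errors are 8%, 9% and 9%.

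2. Replace the parenthesis with the actual allowance:

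> 20/(1 − 0.38) = 32.3, so at least 33 are needed; 34 are planned, which leaves about 21 evaluable at 12 months.

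The sponsor should also state who counts in the denominator of each primary endpoint. If all 34 treated patients are to be analysed, quote 99.1%, 99.97% and 99.95%, with standard errors of 5.8%, 7.0% and 6.9%, in place of the figures in the first change.

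The cost is a text correction. Enrolment, thresholds and analysis stay as they are.
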